3.0 PATIENT ELIGIBILITY

3.1 Conditions for Patient Eligibility

- 3.1.1 Patients must have histologically proven adenocarcinoma of the rectum with no evidence of distant metastases.
- 3.1.2 The tumor must be clinically Stage II (T3-4 N0) or stage III (N+). Stage of the tumor may be determined by CT scan, endorectal ultrasound or MRI. (For patients receiving chemotherapy prior to protocol chemoradiation, the initial clinical stage applies. CT/MRI/PET should be performed within 2 months of study entry to exclude disease progression.) For the MTD expansion phase only: patients who are stage IV, and in whom it is planned to administer capecitabine and radiation then have a resection of their rectal cancer, are also eligible. Submit documentation to BrUOG on location of metastatic disease sites with source confirmation (scan, pathology etc) and obtain confirmation that patients would meet this criterion.
- 3.1.3 Measurable disease not required at baseline. Patient's without measurable disease may be enrolled as long as they clinically meet stage II or III criteria or for MTD expansion phase: also stage IV.
- 3.1.4 Patients must not have received pelvic radiation for rectal cancer, or prior pelvic radiation for any other malignancy that would prevent the patient from receiving the required radiation treatments for this study. (Patients may receive neoadjuvant chemotherapy prior to study chemoradiation)
- 3.1.5 Patients must not have an active concurrent invasive malignancy. Patients with prior malignancies, , are eligible if they are deemed by their physician to be at low risk for recurrence. For example, patients with squamous or basal cell carcinoma of the skin, melanoma in situ, carcinoma of the cervix, early stage breast cancer, or carcinoma in situ of the colon that have been effectively treated are eligible, even if these conditions were diagnosed within 3 years prior to registration.
- 3.1.6 Patients must be \geq 18 years of age,
- 3.1.7 ECOG performance status 0-1

3.1.8 ANC \geq 1,000/µl, platelets \geq 100,000/µl, total bilirubin \leq ULN (except for patients with Gilbert's syndrome who may only be included if total bilirubin is \leq 3xULN with direct bilirubin within normal range),

ALT \leq 2.5xULN, AST \leq 2.5xULN,

fasting plasma glucose \leq 140 mg/dL and HbA1c \leq 6.4% (both criteria have to be met),

 $HGB \ge 9.0g/dL$.

Serum creatinine < 1.5xULN and/or creatinine clearance > 50% LLN

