Three patients will be accrued to level 1. If dose level 1 is not tolerated then dose level -1 will be investigated. If no dose limiting toxicities are observed following completion of BYL719, capecitabine and radiation, and after patients are observed for 2 weeks post completion, then accrual to level 2 will proceed. If a DLT is observed in one of the first 3 patients in a dose level, then accrual for that level will be expanded to 6 patients. Two or more instances of DLT in a cohort of 6 patients will result in the preceding dose level being defined as the MTD. After determination of the MTD, the final cohort will be expanded so that a total of 24 patients are treated on study. A patient will be considered inevaluable if they receive <67% of their total intended treatment (BYL719, Capecitabine or Radiation) for non-protocol required reasons.

During the MTD dose finding portion, patients who are removed from study for reasons other than a DLT, defined in section 5.2, will be replaced.

If a dose limiting toxicity occurs, BYL719 will be held until the toxicity reduces to \leq grade 1 at which point patients will be permanently dose reduced by 1 dose level. Patients may continue to receive their capecitabine and radiation as per institutional standard of care when toxicities resolve to \leq grade 2.

If treatment is held for more than 28 days, then patient should come off study. Definition of Dose Limiting Toxicities

- Grade 4 neutropenia (ANC < 500/mm³)
- ANC $<1000/\text{mm}^3$ with fever (temp > 101) or infection
- Grade 4 thrombocytopenia: Platelets <25,000/mm³
- Platelets <50,000/mm³ requiring transfusion
- Grade 3 or 4 treatment related non-hematologic toxicities excluding alopecia. Grade 3 nausea, vomiting or diarrhea will only be considered a dose limiting toxicity if it occurs for greater than 48 hours despite maximal medical support. Grade 3 electrolyte abnormalities will not be considered dose limiting toxicities if the electrolyte disorder can be corrected to grade 2 or less within 72 hours. A grade 4 electrolyte abnormality will be considered a DLT.
- Patients who receive < 67% of intended BYL719 or capecitabine secondary to treatment related toxicities will also be considered as having a DLT (patients will be considered inevaluable)

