5.2 Definition of Dose Limiting Toxicities

- Grade 4 neutropenia (ANC < 500/mm³)
- ANC $<1000/\text{mm}^3$ with fever (temp > 101) or infection
- Grade 4 thrombocytopenia: Platelets <25,000/mm³
- Platelets <50,000/mm³ requiring transfusion
- Grade 3 or 4 treatment related non-hematologic toxicities excluding alopecia. Grade 3 nausea, vomiting or diarrhea will only be considered a dose limiting toxicity if it occurs for greater than 48 hours despite maximal medical support. Grade 3 electrolyte abnormalities will not be considered dose limiting toxicities if the electrolyte disorder can be corrected to grade 2 or less within 72 hours. A grade 4 electrolyte abnormality will be considered a DLT.
- Patients who receive < 67% of intended BYL719 or capecitabine secondary to treatment related toxicities will also be considered as having a DLT

During the MTD dose finding portion, patients who are removed from study for reasons other than a DLT, defined in section 5.2, will be replaced.

5.3 Management of Specific Toxicities are outlined below for all patients: most conservative assessments must be used for management and modification:

If a dose limiting toxicity occurs, BYL719 will be held until the toxicity reduces to \leq grade 1 at which point patients will be permanently dose reduced by 1 dose level. Patients may continue to receive their capecitabine and radiation as per institutional standard of care when toxicities resolve to \leq grade 2.

If treatment is held for more than 28 days, then patient should come off study.

During the MTD dose finding portion, patients who are removed from study for reasons other than a DLT, defined in section 5.2, will be replaced.

For toxicities other than dose limiting toxicities, specific dose adjustments, based on the worst preceding toxicity as graded by the NCI Clinical Toxicity Criteria ([NCI-CTCAE version 4.03]), are described below. A maximum of 1 dose reduction of BYL719 from the starting dose may be allowed.

Missed doses of BYL 719 are not made up and BYL719 will be stopped when radiation is completed.

Dose Modifications for BYL719 (TREATMENT RELATED (BYL719)): This table only applies once patient has begun treatment on study and it is only applicable while they are receiving treatment on study		
Worst toxicity (CTCAE 4.03 Grade)	Dose Modifications for BYL719	
HEMATOLOGICAL		
Neutropenia (ANC)		
Grade 3 (ANC < 1.0 - 0.5 x 10 ⁹ /L)	Omit dose until resolved to ≤ Grade 1, then:	

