17.0 STATISTICS

Sample Size Justification:

Three patients will be accrued to level 1. If no dose limiting toxicities are observed following completion of BYL719, capecitabine and radiation, and once the 2 week post treatment completion assessment is performed, then accrual to level 2 will proceed. If a DLT is observed in one of the first 3 patients in a dose level, then accrual for that level will be expanded to 6 patients. Two or more instances of DLT in a cohort of 6 patients will result in the preceding dose level being defined as the MTD. After determination of the MTD, the final cohort will be expanded to treat a total of 24 patients on the entire study. During the dose escalation phase, if 3 or more patients have a DLT or there is one grade 5 treatment-related serious adverse event that occurs, protocol accrual will be suspended. If this circumstance occurs, the Brown University Oncology Research Group data safety monitoring Chair will review the adverse event data and make

appropriate recommendations to the Brown University Oncology Research Group and the FDA about the study. Sample size: Approximately 24.

Threshold To Bring BYL719 Forward With Capecitabine and Radiation in Rectal Cancer: The primary goal of this Brown University Oncology Research Group is to determine that a safe dose of BYL719 can be administered with capecitabine and radiation in patients with rectal cancer. *Therefore, the threshold of success for this phase I study is to establish safety.* In a subsequent NRG study, within the TNT framework, a randomized phase II study will be planned exclusively in patients with PIK3CA mutations to assess whether pathologic complete response is improved within this specific subgroup of patients.

A patient will be considered inevaluable if they receive <67% of their total intended treatment (BYL719, Capecitabine or Radiation) for non-protocol required reasons.

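### The automatic accrual suspension in Section 17.0 stops at the end of dose escalation, so a treatment-related death in the expansion does not pause accrual; the text also leaves the DLT count unclear

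*Combined protocol and SAP*

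**What the plan says.** Section 17.0 contains the plan's only automatic stop on accrual. It opens "During the dose escalation phase, if 3 or more patients have a DLT or there is one grade 5 treatment-related serious adverse event", and the consequence is suspension followed by review and recommendations from the data safety monitoring Chair. The opening words govern both triggers. Section 4.1 repeats the cohort rules without any suspension rule.

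The expansion comes later: "After determination of the MTD, the final cohort will be expanded to treat a total of 24 patients on the entire study". Eligibility widens at that point, since Section 3.1.2 has a clause that begins "For the MTD expansion phase only: patients who are stage IV". Section 17.0 also says that "the threshold of success for this phase I study is to establish safety".

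Three passages bear on who counts in the DLT rate:

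- Section 4.1, last item of the DLT definition: patients below 67% of intended BYL719 or capecitabine "secondary to treatment related toxicities will also be considered as having a DLT (patients will be considered inevaluable".
- Section 5.2, the same item: "Patients who receive < 67% of intended BYL719 or capecitabine secondary to treatment related toxicities will also be considered as having a DLT", with no remark about evaluability.
- Section 17.0, and the same sentence in Section 4.1: "A patient will be considered inevaluable if they receive <67% of their total intended treatment (BYL719, Capecitabine or Radiation) for non-protocol required reasons".

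Sections 4.1, 5.2 and 5.3 add that, in dose finding, patients removed for reasons other than a DLT are replaced.

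**The concern.** In escalation, one treatment-related death halts accrual automatically. In the expansion the same event does not, although at least half of the patients at the chosen dose are treated there and stage IV patients enter only there. Escalation therefore provides no DLT experience in stage IV disease. The plan gives no reason for dropping the hold.

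The second issue is the count itself. Establishing safety is the stated threshold of success, so the DLT rate at the MTD is the number that readers will use. If patients whose DLT is toxicity-driven under-dosing can be set aside as inevaluable, that rate is biased downward. If the trigger of three patients has two readings, the same data may or may not suspend the trial.

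**Working it through.** **1. Size of the expansion.** The plan gives no derivation for 24, so there is no sample-size formula to reproduce. Inputs from Sections 4.1 and 17.0: total 24; a level passes on 0/3 or on 1/6; a level fails on at least 2 DLTs in six; levels 1 to 3, with level -1 if level 1 fails. Assumptions: the expanded cohort is the MTD level (level 3 if all pass), no replaced patients are among the 24, and a failing level uses six patients. Expansion = 24 minus patients used in escalation.

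| Escalation outcome (levels in order) | Used | Expansion | Total at MTD | Minimum DLTs before expansion |
|---|---|---|---|---|
| 1 fails; -1 passes 0/3 | 9 | 15 | 18 | 2 |
| 1 fails; -1 passes 1/6 | 12 | 12 | 18 | 3 |
| 0/3; 2 fails | 9 | 15 | 18 | 2 |
| 1/6; 2 fails | 12 | 12 | 18 | 3 |
| 0/3, 0/3; 3 fails | 12 | 12 | 15 | 2 |
| 0/3, 1/6; 3 fails | 15 | 9 | 15 | 3 |
| 1/6, 0/3; 3 fails | 15 | 9 | 12 | 3 |
| 1/6, 1/6; 3 fails | 18 | 6 | 12 | 4 |
| All pass, none with 1/6 | 9 | 15 | 18 | 0 |
| All pass, one level with 1/6 (3 paths) | 12 | 12 | 15 or 18 | 1 |
| All pass, two levels with 1/6 (3 paths) | 15 | 9 | 12 or 15 | 2 |
| All pass, all 1/6 | 18 | 6 | 12 | 3 |

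That is 8 + 1 + 3 + 3 + 1 = 16 paths. The expansion is 6, 9, 12 or 15 patients. Its share of patients at the MTD runs from 6/12 = 50% to 15/18 = 83%. The text does not say what follows 2 or 3 DLTs in a level's first three patients. If such a level fails at three, escalation can use as few as 6 patients, and the expansion reaches 18 of 21 at the MTD.

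**2. How often the missing hold would matter.** The documents give no rate of treatment-related death, so the rates here are assumptions. P(at least one death) = 1 - (1 - r)^n.

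| Assumed r | n = 6 | n = 15 |
|---|---|---|
| 1% | 0.06 | 0.14 |
| 2% | 0.11 | 0.26 |
| 5% | 0.26 | 0.54 |

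**3. Per level or cumulative.** A passing level has at most one DLT. On a per-level reading, the trigger can therefore fire only at a level that the MTD rule has already failed at two. On a cumulative reading, the last column shows six of the 16 paths that always reach three DLTs before expansion, including both routes to a 6-patient expansion. One of those is the path on which every level passes with 1/6. Three more paths have a minimum of two but include a failing six. On the literal wording a failing six holds 2 to 4 DLTs (one in the first three, then one to three more), so these paths can also reach three. The total is at least 6 and up to 9 of 16.

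**4. The inevaluable remark.** Under-dosing because of toxicity is a DLT in both Section 4.1 and Section 5.2. The general inevaluable rule is confined to reasons that the protocol does not require, and dose holds for toxicity are required by the protocol. The remark in Section 4.1 therefore fits neither Section 5.2 nor the general rule. Taken literally, removing k patients with a DLT turns x/n into (x - k)/(n - k), which is lower whenever x < n. With invented counts, to show direction only: 5/18 = 28% (exact 95% CI 10% to 53%) becomes 3/16 = 19% (4% to 46%) if two are removed.

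**The case against.** The strongest reply is that the expansion is already supervised. Section 16.0 has the DSMB review all adverse events, meet twice a year and when needed, and consider change or termination. Sections 11.3.2 and 11.6 require deaths thought related to the study drug to be reported within 24 hours. The patient-level rules apply throughout ("Management of Specific Toxicities are outlined below for all patients"), and Section 15.6 allows closure for unacceptable risk. Even in escalation, the trigger leads only to review and recommendations. All of this stands. It narrows the gap to one thing: in the expansion, accrual need not stop while the review takes place.

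A second reply is that the MTD is fixed before the expansion begins. That is also right. A reader might infer that the expansion is meant to confirm the MTD, particularly since 0/3 and 1/6 leave one-sided 95% upper limits of 63% and 58% for the DLT rate. The protocol makes no such claim, and those limits apply to any 3+3 design.

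Third, Section 4.1 does say that the under-dosed patients have a DLT, and the replacement rule does not replace patients removed for a DLT. That protects the escalation decisions to a large extent. It does not settle the reported rate, and the replacement rule covers only dose finding.

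**Conclusion.** The point holds in a limited form. The automatic suspension does not reach the expansion, which on the literal wording is 6 to 15 patients and 50% to 83% of those at the MTD. The size rests on the assumptions in the path table; the textual gap does not. The inevaluable remark contradicts Section 5.2 and the general rule, and the count of three is undefined.

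Three stronger readings are not supported. A reader might infer that the expansion lacks safety oversight; the review and reporting provisions show otherwise. A reader might infer that patients with a DLT will be dropped from the rate; no passage says that they leave the denominator, and the remark only makes this possible. A reader might infer that a numerical DLT boundary is needed in the expansion; the plan states no target DLT rate against which to set one, so that choice is the sponsor's. This is worth correcting because the remedy is cheap and bears on the primary objective, but it does not undermine the design.

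**What to change.** 1. Extend the existing Section 17.0 suspension and Chair review to the expansion for any treatment-related grade 5 event. The cost is an occasional pause in accrual, including for events that review then judges acceptable.
2. Reconcile the inevaluable remark in Section 4.1 with Section 5.2 and with the general rule in Sections 4.1 and 17.0, so that every patient with a DLT stays in both numerator and denominator. Report the DLT rate with an exact 95% confidence interval for all patients treated at the MTD, with the expansion-only rate beside it. The second figure is needed because the pooled rate includes the escalation patients whose results selected the dose. Present both as descriptions of safety at a dose already set by the 3+3 rule.
3. State whether the trigger of three patients is counted per level or cumulatively across escalation.

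All three are wording changes in a short amendment. Section 6.0 already schedules toxicity assessment for every patient, so no extra patients, visits or data are required.

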(y/n) Ability to comply with protocol and study follow-up procedures
(y/n) QTcF \leq 480 msec
(y/n) Patients history of diarrhea has been review and patient has been informed of potential
study drug induced diarrhea and management.
Exclusion Criteria:
(y/n) Patients must not have received pelvic radiation for rectal cancer, or prior pelvic radiation for any other malignancy that would prevent the patient from receiving the required radiation treatments for this study. (Patients may receive neoadjuvant chemotherapy prior to study chemoradiation)
(y/n) Patients must not have an active concurrent invasive malignancy. Patients with prior malignancies , are eligible if they are deemed by their physician to be at low risk for recurrence. For example, patients with squamous or basal cell carcinoma of the skin, melanoma in situ, carcinoma of the cervix, early stage breast cancer, or carcinoma in situ of the colon that have been effectively treated are eligible, even if these conditions were diagnosed within 3 years prior to registration.
(y/n) Patient with impaired gastrointestinal (GI) function or GI disease that may significantly alter the absorption of oral BYL719 (e.g. ulcerative disease, uncontrolled nausea, vomiting, diarrhea, malabsorption syndrome, or small bowel resection). Patients with colostomies are allowed unless colostomy is for one of the precluded reason above.
(y/n) Suspected or confirmed metastatic disease including CNS involvement. See section 3.1.2 for stage IV patient eligibility.
(y/n) Prior hypersensitivity to any of the excipients of BYL719 (alpelisib)
(y/n) Patient who has undergone major surgery \leq 4 weeks prior to starting study treatment or in the investigators opinion who has not recovered from side effects of such procedure
(y/n) Patient with clinically manifest diabetes mellitus, or documented steroid induced diabetes mellitus
(y/n) Patient who has not recovered to grade 1 or better (except alopecia) from related side effects of any prior antineoplastic therapy
(y/n) Patient who has had systemic therapy within 4 weeks (6 weeks for nitrosoureas or mitomycin C) prior to study treatment (BYL719 drug)
(y/n) Patient has a clinically significant cardiac disease or impaired cardiac function. See eligibility for more details)

(y/n) QTcF interval > 480 msec on screening ECG
(y/n) Patient who is currently receiving medication with a known risk of prolonging the QT interval or inducing Torsades de Pointes (TdP) and the treatment cannot either be discontinued or switched to a different medication prior to starting study drug treatment. To be documented and submitted to BrUOG with registration.
(y/n) Patient who has participated in a prior investigational cancer treatment study within 30 days prior to enrollment. This refers to treatment not follow-up.
(y/n) Patient with known positive serology for human immunodeficiency virus (HIV)
(y/n) Patients who have other concurrent severe and/or uncontrolled medical conditions tha would, in the Treating Physician's judgment, contraindicate patient participation in the individual patient program (eg. active or uncontrolled severe infection, chronic active hepatitis, immuno-compromised, acute or chronic pancreatitis, uncontrolled high blood pressure, interstitial lung disease, etc.) (y/n) Patient with any other condition that would, in the Investigator's judgment, preclude patient's participation in the clinical study due to safety concerns or compliance with clinical study procedures, e.g. infection/inflammation, intestinal obstruction, unable to swallow oral medication, social/psychological complications, chronic active hepatitis, severe hepatic impairment etc
(y/n) Patient has a history of non-compliance to medical regimen or inability to grant consent
(y/n) Patient is currently receiving treatment with drugs known to be strong inhibitors or inducers of isoenzyme CYP3A or that prolong QT interval (see eligibility for more details.
(y/n) Patient is currently receiving warfarin or other coumarin derived anti-coagulant, for treatment, prophylaxis or otherwise. Therapy with heparin, low molecular weight heparin (LMWH), or fondaparinux is allowed
(y/n) Pregnant or breastfeeding. Women of child bearing potential must have a negative serum or urine pregnancy test (<5mIU/mL) within 14 days prior to beginning of treatment. Postmenopausal women do not need to have a pregnancy test, please document status. See eligibility for more details. See exclusion for definition of post-menopausal.
(y/n) Patient who does not apply highly effective contraception during the study and through the duration as defined below after the final dose of study treatment as defined in eligibility
(y/n) Herbal preparations/medications are not allowed throughout the study. These herbal medications include, but are not limited to: St. John's wort, Kava, ephedra (ma huang), gingko biloba, dehydroepiandrosterone (DHEA), yohimbe, saw palmetto, medical marijuana and ginseng Patients need to stop using these herbal medications 7 days prior to first dose of study drug

(y/n) Patient must not eat or drink Seville orange (and juice), grapefruit or grapefruit juice, grapefruit hybrids, pummelos, starfruits and cranberry juice from 7 days prior to the first dose of study drug and during the entire study treatment				
day 1 of study drug, or who has corticosteroids are permitted: sir obstructive airways diseases), et	not fully recovered from single doses, topical applicat	, -		
as the consent form and this che	cklist, must be faxed to the	e study parameters section of this study, as well e BrUOG Central Office at the time of n "Not Enclosed," or check if "Not Applicable."		
1) Eligibility Form	EnclosedNot Enclosed	Not Applicable		
2) Heme/Onc initial note	EnclosedNot Enclosed	Not Applicable		
3) Pathology Report(s)	EnclosedNot Enclosed	Not Applicable		
4) MRI/CT Report(s)	EnclosedNot Enclosed	Not Applicable		
5) Lab Source Document	EnclosedNot Enclosed	Not Applicable		
6) ICF signature page				
7) Other documents, please list_		 		
IRB approval date of protocol:				
Hospital where patient will be treated with Oncologist:				
Location where radiation will be given:				
Date patient will begin treatmen	nt Capecitabine:			
Date patient will begin treatmen	at BYL719:			
Date patient will begin treatment Radiation:				
Primary Physician:				

Radiation Oncologist:

Your signature:	

